1.0 Objectives

1.1 *Describe the purpose, specific aims, or objectives.*

Purpose: Increase physical activity (PA) in children with ADHD using a novel, family-based intervention that promotes PA within the context of evidence-based behavioral management training (BMT) for parents, enhanced with mobile health (mHealth) behavior change strategies.

Specific Aims:

- 1) Test the feasibility and acceptability, of an 8-week, family-based, multi-level intervention (BMT-Health) to promote PA in young children with ADHD
- 2) to derive an estimate of the effect size of the intervention on PA

1.2 *State the hypotheses to be tested.*

The BMT-Health intervention will be feasible and acceptable to families for children with ADHD and will show promise for increasing PA in children with ADHD

2.0 Background

2.1 *Describe the relevant prior experience and gaps in current knowledge.*

[name] (Co-PI) is a clinical psychologist with expertise in psychosocial treatments and health risk behaviors associated with ADHD. She has published on the relationship of ADHD to health risk behaviors,⁶¹ and on health promotion strategies for this population.⁶¹⁻⁶³ She has worked on RCTs of behavioral interventions for ADHD and published outcomes research on prevention programs for high-risk youth.⁶⁴⁻⁶⁶ She collaborated with [name] (co-I) to complete a study using the proposed technological and social media components of the BMT-Health intervention (wearable activity tracker, Facebook engagement intervention) that was found to increase PA in adolescents with ADHD across a 4-week period.¹⁴

[name] (Co-PI) is a general pediatrician and PA researcher with a K23 Career Development Award focused on promoting PA and outdoor time in early childhood, with an emphasis on the neurocognitive benefits of PA. She and her team have considerable experience collecting data via accelerometry and in community based interventions to promote PA in children. This work formed the basis of an R21/R33 application that was funded and will support a PA intervention in preschool children using mHealth technology.

- 2.2 This study will combine the use of mHealth wearable technology (Garmin vivofit) for children and caregivers, with a social media program (Facebook group) for caregivers, delivered through and integrated in a BMT program for a technologically and theoretically integrated, multi-level intervention approach. This proposal

represents the first study examining such an intervention to increase PA levels and improve health and functioning in children with ADHD. *See section 2.2 for details of team's prior research. Describe any relevant preliminary data.*

National Survey of Children's Health: Using nationally representative data from two time points over the past decade, we found that children with ADHD are at high risk for engaging in inadequate PA.¹¹ Only about a third of children with ADHD were reported to have had 20 minutes/day of MVPA in the previous week. Also, less than half of children with ADHD participated in sports in the past year. Children with more severe ADHD, lower SES, and obesity had lower odds of sports participation, which is not surprising but concerning, as these children are also at higher risk for comorbidities and health disparities. Of note, medication use in ADHD was not associated with sports participation or achieving daily PA. Our findings highlight the need to focus on children with ADHD as a high-risk group for poor health behaviors. The abstract for this study has been accepted for presentation at the American Academy for Child & Adolescent Psychiatry Annual Meeting in 2017, and this paper is currently under review.

Clinic survey results: We developed and piloted a self-report survey data from 44 caregivers of children being seen for ADHD concerns in the Program to Enhance Attention Regulation and Learning (PEARL Clinic) at Seattle Children's Hospital. The measure was administered to all families seen for new evaluations in the PEARL Clinic during a 2-month time frame in the spring of 2017. Less than 12% of parents reported that their children engaged in >60 minutes of PA/day on 7 days/week. Seventy-six percent of parents reported that their child had 2 or fewer days of physical education at school/week. The most commonly identified barriers for their children to engage in PA activity were 1) does not do well in groups/needs 1:1 supervision, 2) not enough time, and 3) no interest (by child). Only 33% of responding parents reported that they themselves achieved the 150 minutes/week of PA recommended for adults. Eighty-one percent of parents said they would be potentially interested in participating in a program to increase their child's PA, and 88% said they would be interested in an activity tracker for their child. These survey results highlight both need for, acceptability, and local interest in a PA intervention for our families with children who have ADHD.

Teen ADHD Fitbit study: Drs. [name] (PI) and [name] (co-I) recently published a pilot study of an intervention to increase PA in adolescents (ages 14-18) with ADHD. Participants wore an activity tracker paired with a smartphone app, participated in a Facebook group, and received brief health coaching focused on PA goal setting. Across 4-weeks, adolescents significantly increased their daily PA, and trends were observed of improvement in self- and parent-reported ADHD symptoms.¹⁴ [name] has also completed pilot trials of the proposed technological methodology (activity tracker, Facebook group, accelerometry)

measurement), finding good feasibility and acceptability in non-clinical groups of adolescents⁷² and adolescent cancer survivors.¹⁵

2.3 *Provide the scientific or scholarly background for, rationale for, and significance of the research based on the existing literature and how will it add to existing knowledge.*

Attention Deficit Hyperactivity Disorder (ADHD) is a common pediatric disorder associated with persistent and wide-ranging impairments and negative health outcomes, including obesity and Substance Use Disorders (SUDs). An estimated 5-10% of children worldwide have ADHD, which is marked by inattention, impulsivity and/or hyperactivity, and confers risk for difficulties in social, academic, vocational, and home functioning throughout development.^{1,2,18,19} ADHD is associated with health risks such as obesity, which in turn increases chronic health problems and mortality rates.^{20,10} Though stimulant medications improve ADHD symptoms and functioning acutely in the majority of those treated, medication is not recommended as the first-line treatment for young children with ADHD.²² Moreover, many youth do not tolerate or adhere to medication, there are concerns regarding diversion,²³ and longer-term outcomes of medication remain unclear.³ Thus, there is a need for innovative, generalizable intervention approaches that could serve as alternatives or adjuncts to existing treatments and that show promise for altering longer-term developmental and health trajectories.

Physical activity (PA) enhances neurocognitive and self-regulatory development and has been found to decrease ADHD symptoms. There is an emerging but limited literature that both brief and sustained periods of PA are associated with improved executive functions,^{24,25} which are frontal lobe processes such as response inhibition and working memory that are often compromised in ADHD⁷ and feature prominently in theories of ADHD.²⁶ Children with ADHD who participate in moderate-to-vigorous PA (MVPA) in clinic and school settings demonstrate improvement on cognitive tasks measuring sustained attention, response inhibition, stimulus processing, response accuracy, and self-regulation,²⁷⁻³² and also exhibit fewer behavioral symptoms of ADHD and improved reading and math achievement.^{5,33-35} One meta-analysis reported an overall medium effect size (Hedge's $g=0.63$) of PA on ADHD functional outcomes; effects did not vary by PA intensity but increased with PA duration.³⁶ In the only large-scale randomized trial of a PA-intervention for children with ADHD, a 31-minute before-school exercise program improved both parent and teacher ratings of ADHD symptoms across 12 weeks, indicating lasting effects of the intervention throughout the day.³⁵ It should be noted, however, that this trial did not objectively measure PA but instead relied on physical fitness as a proxy measure. Additionally, observational studies have documented a link between PA and "real world" functional outcomes such as scores on standardized achievement tests.^{37,33} Thus, interventions to increase PA for

children with ADHD have demonstrated the potential to improve broader domains of functioning, offering an alternative or supplementary treatment to existing treatment approaches. An acceptable and feasible multi-level, family-based intervention to increase PA of children with ADHD has the potential to improve executive functioning, reduce ADHD symptoms, and promote health, with implications for longer term well-being.

A3. Children with ADHD are at particular risk for not meeting

recommendations for daily PA. Although hyperactivity would seem to increase daily energy expenditure, children with ADHD have been found to have high prevalence of physical inactivity and obesity.¹⁰ These children may encounter unique barriers to adequate PA and sports participation that are related to their diagnosis. For instance, children with ADHD exhibit increased rates of disruptive, noncompliant, and aggressive behavior and poor motivation.¹ Their parents are more stressed³⁸ and tend to use less effective and more negative, punitive, and inconsistent parenting approaches than parents of non-ADHD youth.³⁹ Moreover, parents of children with ADHD have high rates of ADHD, depression, and substance use disorders themselves,⁴⁰ complicating their efforts to implement effective parenting strategies to promote PA. As such, parents of children with ADHD may have considerable difficulty encouraging participation in PA and/or limiting their sedentary behaviors, such as media use.⁴¹ In fact, parents may offer screen time to their child in order to get a break from parenting. Additionally, children with ADHD demonstrate greater rates of oppositional behavior and poor sportsmanship in recreational sports settings, interfering with their engagement and success in sports and reducing overall PA.⁴²

A4. Parenting interventions have been shown to be effective in modifying child behavior and improving ADHD functional outcomes.

Decades of research on behavioral treatments for children with ADHD indicate strongest support for interventions that target parents, caregivers, and teachers rather than children directly.^{43,44} Behavioral Management Training (BMT) for ADHD teaches parents to implement contingency management procedures to target the behavioral and functional problems associated with ADHD, most often by using behavior change strategies such as special playtime, differential attention, praise, incentives, and effective consequences to foster child skill development and behavior change.⁴⁵ Such interventions yield reductions in children's oppositional and aggressive behavior, increase parent use of positive parenting strategies, and reduce parent criticism and conflict.^{46,47} However, such programs focus primarily on reducing noncompliance and parenting stress, whereas no evidence currently exists on how these strategies impact health behaviors such as PA. Furthermore, such programs were developed over 30 years ago, prior to the internet, WIFI, and cultural changes affecting the current context of parent-child interactions. We hypothesize that enhancing and augmenting evidence-based BMT strategies (e.g., special playtime, praise,

incentive systems) to additionally target PA in ADHD youth will increase measured PA and subsequently yield even greater improvements in ADHD symptoms and overall functioning than current treatments alone.

Summary of Scientific Premise: Increasing PA is associated with improvements in executive functions, ADHD symptoms, and broader academic and social functioning.^{5,34} **Therefore, family-based interventions to increase PA in ADHD youth could substantially improve ADHD-related functioning if integrated with existing evidence-based parenting interventions for ADHD, and may also reduce risk for negative health outcomes..**

3.0 Inclusion and Exclusion Criteria

3.1 *Describe how individuals will be screened for eligibility.*

Prior to the screening visit, participants will complete a pre-screening interview over the phone with one of the study staff. The study staff will conduct the interview using a phone screen script. If the subject is eligible then potential participants and their caregiver will attend an initial screening visit to confirm ADHD diagnosis and global severity. Eligible children will then complete a two-step screening procedure for low PA participation (caregiver-report survey of daily PA and a 3-day accelerometer wear) to determine level of daily PA.

Describe the criteria that define who will be included or excluded in your final study sample.

Inclusion criteria for children:

- age 5-10 years
- ADHD diagnosis
- engage in <5 days of vigorous physical activity for more than 60 minutes at a time based on parent report
- CGI-S rating >4 and <7
- One adult caregiver willing to participate in the study and complete baseline/follow-up measures

Inclusion criteria (for participating caregiver):

- willing to participate in the study and complete baseline/follow-up measures
- able to complete forms in English
- owns a smart phone or similar Garmin compatible mobile device (e.g. iPod Touch) or willing to borrow iPod from study coordinators during the study period
- Agree to install and share data from the Garmin smart phone app with investigators

Inclusion criteria (for supplemental caregiver)

- caregiver to child already participating in study

Child Exclusion Criteria:

- younger than 5 years old or older than 10 years old
- do not meet criteria for ADHD diagnosis
- per caregiver report, engage in >60 min/day of MVPA consistently for at least 5 days per week
- Meet diagnostic criteria for psychiatric co-morbidities including Autism Spectrum Disorder, Depressive Disorder, Mood Disorder, Psychotic Disorder, or Intellectual Disability that could interfere with intervention uptake
- currently taking psychotropic medications that may decrease ability to engage in PA (e.g. Alpha 2 agonists during the day). Children receiving stimulant medications who are on a stable dose for the past 30 days will be eligible for participation
- any physical or medical restrictions on PA
- Child currently/Previously used a wearable physical activity sensing device the majority of days for a 2 month period in the past year

Caregiver Exclusion Criteria:

- Caregiver participated in an evidence-based parent behavior management training program (i.e., Incredible Years, Triple P, PCIT, Barkley's Defiant Child) in the past 24 months.

3.2 *Indicate specifically whether you will include or exclude each of the following special populations: (You may not include members of the above populations as subjects in your research unless you indicate this in your inclusion criteria.)*

- Adults unable to consent - excluded
- Individuals who are not yet adults (infants, children, teenagers) - included
- Wards of the state - excluded
- Pregnant women - Excluded
- Prisoners – excluded

3.4 Screening Visit

Screening visits will be completed within 60 days of group treatment start. Eligible participants will be enrolled on the same day as the screening visit.

Diagnostic evaluation will consist of structured interviewing with the child and caregiver on the *Schedule for Affective Disorders for School-Aged Children (K-SADS) Present and Lifetime Version (K-SADS-PL)*,[35] which assesses current and past presence of DSM-5 disorders in ages 6-18. Interviewing will be completed by a licensed psychologist or supervised pre- or post-doctoral trainee. The K-SADS-PL has strong test-retest and inter-examiner reliability, with kappas for ADHD above .70.[36] Inter-examiner reliability will be established and monitored over the trial by taping interviews and randomly selecting 20% for reliability checks. Should kappas fall < .70, additional training will be provided.

The Clinical Global Impressions (CGI-S) ADHD Severity Scale,^[37] a clinician-rated, 7-point scale that describes the severity of ADHD symptoms (using the K-SADS), will be used to screen for ADHD severity. Children must have a current CGI-S rating >4 to participate. The CGI-S also serves as an exploratory outcome in the R21 phase and a secondary outcome in the R33 phase.

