7.0 Study Timelines

7.1 *Describe:*

- *The duration of an individual subject's participation in the study.*
For participants in the BMT-Health group intervention – approx. 9 - 16 weeks from the date of screening/baseline enrollment
- *The duration anticipated to enroll all study subjects.*
Using a rolling recruitment approach, enrollment for the entire study is anticipated to take 2 years.
- *The estimated date for the investigators to complete this study (complete primary analyses)*
The estimated date for completion of this study is January 2020.

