study and completing informed consent/assent and baseline study measures, caregivers will be assigned to an 8-week LEAP intervention group, with 6-8 caregivers per group. Children and caregivers will complete baseline and follow-up assessment batteries at 5 weeks and 9 weeks. Caregivers will participate in a 1-hour focus group regarding their experience in the intervention during week 9. PA will be measured using accelerometry x7 days at baseline and at 9 weeks. The LEAP intervention consists of 3 components: 1) an enhanced 8-week, group-based BMT curriculum, 2) caregiver and child use of the Garmin daily activity tracker accompanied by personalized goal setting, and 3) caregiver participation in a private Facebook group to encourage PA goal achievement and promote social support and positive parenting. All enrolled families will receive 8 weekly group BMT-Health sessions led by either [name] or [name], who have considerable experience leading BMT groups for children with ADHD. Groups will include initial enrollment of 6-8 families, a group facilitator, and a co-facilitator. The curriculum and homework is based on existing evidence-based models, namely Barkley's Defiant Children¹² curriculum, with integrated content specifically focused on promoting PA and addressing barriers to PA. Table 1 presents a sampling of session content, highlighting the unique aspects of the BMT-Health curriculum compared to standard BMT. Later sessions (with related homework) will include topics such as: community resources for PA, challenges encountered and over-coming barriers, using incentives to promote healthy behaviors, role of bedtime routines/sleep, and goal-setting for the future/strategies for sustainability. Information and resources relevant to that week's topic will also be provided via Facebook and text messages. Fidelity to the curriculum will be assessed by trained coders using content checklists in a randomly-selected sampling of session audiotapes. We included the standard Barkley curriculum with this IRB application. We now include an overview of LEAP curriculum sessions 1-8 and how the sessions are similar to and differ from the Barkley curriculum (see separate attachment).

Table 1. BMT Standard and BMT-Health Curricula Overview – Sessions 1-3.

Barkley's Defiant Children¹²					
Strategy Instruction	Homework	Session	BMT-Health		
			Unique Strategy Instruction	Unique Homework	Unique Targets

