- Hip –worn Accelerometer – Actigraph model GT3X+; A small rectangular device housing a tri-axial accelerometer and worn on an elastic belt, the GT3X+ has been used in a number of studies conducted by [name] (Co-PI) research group and a number of other research groups at Seattle Children's. Children will be asked to wear the device with an elastic belt for 7 days on their hip. In order to maximize valid accelerometer data, participants will be asked to wear accelerometers for 24 hours/day, except for water-based activities,[38] and to re-wear accelerometers for another 7-day period if they have < 4 valid days at each measurement time point. The 24-hr wear has been validated for use to collect sleep data in school age

children, which is an exploratory outcome in this study.[39] While sleep has traditionally been measured with wrist actigraphy, algorithms have been produced, validated, and refined to fully automate the capture of sleep duration for children using 24-hour waist-worn accelerometry.[40] As we plan to use a 24-hour waist-worn accelerometer protocol to maximize compliance for the PA data, we will also be able to capture quantitative sleep data on our participants for a broader perspective on these related health behaviors.

Digit Span task asks children to repeat strings of numbers of increasing length forward, then backwards.

- *Stop Signal Reaction Time (SSRT):* In this computerized task, the participant must respond to an arrow stimulus, by selecting one of two options, depending on the direction in which the arrow points. If an audio tone is present, the subject must withhold making that response (inhibition). The test consists of two parts: In the first part, the participant is introduced to the test and told to select the left-hand button when they see a left-pointing arrow and the right-hand button when they see a right-pointing arrow. There is one block of 16 trials for the participant to practice this. In the second part, the participant is told to continue selecting the buttons when they see the arrows but, if they hear an auditory signal (a beep), they should withhold their response and not select the button. The total task requires 15-20 minutes to complete.

Table 2 – Study Measures and Assessments

Construct	Measure	Rater	Source	Screening	Baseline	5 weeks	9 weeks
ADHD diagnosis	K-SADS-PL	P/C	CR	X			
ADHD severity	CGI-S	Clinician	CR	X			X
PA, Sleep	MVPA, light & sedentary time, Step count, sleep duration x 7 days	G/C/A	E		X		X

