Feasibility	Garmin (wear time), Facebook likes and comments	G/P/C	E, SE			X	X
Acceptability	Attendance, TAI	P	CR, DP			X	X
Acceptability	CSQ, Focus group		DP				X
Executive function	SSRT, DS, BRIEF-2	C/P	SE		X		X
ADHD symptoms	Conners-3 (P), Vanderbilt (T)	P/T	DP		X		X
Functional impairment	IRS	P/T	DP		X		X
Parenting	APQ	P	DP		X		X
PA, Sleep, Media use	HBS	P	DP		X	X	X
Sleep problems	CSHQ	P	DP		X		X
BMI	Height, weight	C	SE		X		X
Complementary/Alternative medicine use	HBS	P	DP		X		X
Media Use	Problematic Media Use	P	DP		X		X
Medication use	HBS	P	DP		X	X	X
Mindfulness	Mindful Attention Awareness		DP		X	X	X

	Scale							
Socio-demographics	Survey	P	DP			X		

APQ = *Alabama Parenting Questionnaire*. BMI = *Body Mass Index*. BRIEF = *Behavior Rating Inventory of Executive Function*. CGI-S = *Clinician Global Impressions Scale – Severity*. Conners-3 = *Conners-Third Edition*. CSHQ = *Children's Sleep Habit Questionnaire*. CSQ = *Client Satisfaction Questionnaire*. DS = *Digit Span task*. ERC = *Emotion Regulation Checklist*. FW = *Finger Windows task*. HBS = *Health Behaviors Survey*. IRS = *Impairment Rating Scale*. K-SADS-PL = *Kidnie-SADS-Present and Lifetime Version*. MVPA = *Moderate-to-Vigorous Physical Activity*; PA = *Physical Activity*. SSRT = *Stop-Signal Reaction Time task*. TAI = *Treatment Adherence Inventory*. A = *Actigraph GT3x+*; C = *Child*; G = *Garmin Device*; P = *Parent*; T = *Teacher*. DP=digitally entered by parent/caregiver; CR=Clinician rated; E=electronic device data; SE =study staff entered

For the K-SADS instrument:

- the Pregnancy and Birth Questions will not be included
- the Family History for Biological Relatives will not be included

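### Does using the CGI-S as both entry threshold and exploratory outcome call for a change to the plan?

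*Combined protocol and SAP*

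**What the plan says.** The CGI-S has two roles in the combined protocol and SAP.

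- **Entry filter.** The inclusion criteria in section 3.1 require "CGI-S rating >4 and <7". Section 3.4 restates only the lower bound: "Children must have a current CGI-S rating >4 to participate". It describes the scale as a 7-point clinician rating "that describes the severity of ADHD symptoms (using the K-SADS), will be used to screen for ADHD severity".
- **Outcome.** Section 3.4 adds: "The CGI-S also serves as an exploratory outcome in the R21 phase and a secondary outcome in the R33 phase".

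In Table 2 (section 9.2) the "ADHD severity" row is marked at screening and at 9 weeks, with no baseline or 5-week rating. The K-SADS, on which the rating draws, is marked at screening only.

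The study has one arm. Section 9.1 says: "All enrolled families will receive 8 weekly group BMT-Health sessions". Section 7.1 puts participation at "approx. 9 - 16 weeks from the date of screening/baseline enrollment".

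Section 1.1 sets two aims: feasibility and acceptability, and an effect-size estimate for physical activity. Section 11 makes feasibility and acceptability the main outcome, prefers estimates to formal tests, places the pre-post comparison under the physical-activity aim, and describes the analyses as primarily descriptive. It does not mention the CGI-S.

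**The concern.** Children enter because their screening rating was high, and that rating is also the only pre-treatment CGI-S value. Part of a high rating is rating error or a passing bad spell, so a second rating tends to fall back towards the average of the children screened, even with no intervention effect. With no comparison group, this fall cannot be told apart from a treatment effect or from natural change over the weeks between the ratings.

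The most that is at stake is that a drop in CGI-S could be read as promise for ADHD severity, or be carried into the R33 phase, where the scale is a secondary outcome. Calling the analyses descriptive does not by itself tell a reader that the starting value was selected.

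**Working it through.** The plan gives no CGI-S mean, SD, reliability or expected change, so there is no figure of its own to reproduce. The check asks how large the artefact could be, and whether anything in the plan limits it.

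**Inputs from the document**
- Entry window: 5 or 6 (section 3.1).
- 45 families recruited to give 30 enrolled after screening (section 25.0).
- Up to 45 screened for low activity to give 30 (section 11.1).

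**Assumed inputs**
- Mean μ among screened children: 4.0 to 5.75.
- SD σ: 0.8 to 1.2.
- Reliability ρ: 0.5 to 0.9.
- Severity normally distributed, rating errors independent, no true change. Rater error that persists acts like a higher ρ and shrinks the artefact.

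**Step 1: size of the artefact.** A rating of 5 or 6 means an unrounded score between 4.5 and 6.5. Let m be the mean unrounded score of those who qualify. Then approximately:

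expected change = [μ + ρ(m − μ)] − (mean qualifying rating)

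Example with μ = 4.5, σ = 1, ρ = 0.7:
- P(5) = Φ(1) − Φ(0) = 0.341 and P(6) = Φ(2) − Φ(1) = 0.136, together 0.477.
- Mean qualifying rating = 5 + 0.136/0.477 = 5.285.
- m = 4.5 + (0.399 − 0.054)/0.477 = 5.223.
- Expected second rating = 4.5 + 0.7 × 0.723 = 5.006.
- Change = 5.006 − 5.285 = −0.28, which agrees with simulation (−0.28).

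**Step 2: share of screened children who qualify.**

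yield = Φ((6.5 − μ)/σ) − Φ((4.5 − μ)/σ)

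The table covers σ from 0.8 to 1.2 and ρ from 0.5 to 0.9. Changes come from simulating 2,000,000 children per setting. The last column is the chance that a 95% t interval at n = 30, with no attrition, lies wholly on the improvement side (nominally 2.5%).

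| Screened mean | Yield | Mean change | Interval all improvement |
|---|---|---|---|
| 4.0 | 27%–32% | −0.68 to −0.19 | 32%–99% |
| 4.5 | 45%–49% | −0.45 to −0.13 | 17%–75% |
| 5.0 | 56%–70% | −0.24 to −0.06 | 7%–24% |
| 5.25 | 59%–77% | −0.14 to −0.03 | 4%–9% |
| 5.5 | 60%–79% | −0.04 to 0.00 | 2%–3% |
| 5.75 | 59%–77% | +0.03 to +0.09 | about 1% |

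The sign turns at about 5.5, the middle of the window. Below it, selection mimics improvement; above it, worsening.

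**Step 3: what the planned yield implies.** 30/45 = 66.7%. If the 45 are counted before the CGI-S step, at least that share must score 5 or 6, even if no child fails any other criterion. Means of 4.0 and 4.5 fall short at every SD. These settings meet it:
- mean 5.0 with SD 0.8 (70%);
- means 5.25, 5.5 and 5.75 with SD 0.8 (77%, 79%, 77%);
- means 5.25, 5.5 and 5.75 with SD 1.0 (67%, 68%, 67%).

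Across them the artefact runs from −0.19 to +0.09 points, and the chance of an interval wholly on the improvement side from about 1% to 24%.

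**Step 4: where the plan would use the number.** No section names a CGI-S analysis or draws a conclusion from CGI-S change. The general sentence in section 11 on comparing pre and post outcomes could be stretched to cover it, but it stands within the physical-activity paragraph and is followed at once by the statement that the analyses are primarily descriptive.

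**The case for a change.** The best case for a change is this. The descriptive label limits testing, but it does not remove bias from an estimate, and section 11 says estimates are the focus. The CGI-S is a declared outcome with no rule for reading it, and two sentences would supply one at almost no cost. The yield argument is also not secure. Section 11.1 counts the 45 at the low-activity screen, which section 3.1 places after the CGI-S, and allows more to be screened. On that reading the rows for means of 4.0 and 4.5 remain possible.

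The structural point stands in full, and so does the doubt about which step the 45 refers to. Neither shows that the plan would produce a wrong result. Both CGI-S values would be collected and reported exactly as now; the extra wording would only caution against a reading that the plan never makes. In a single-arm pilot most of that caution (no comparator) applies to every pre-post measure.

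Moving symptom statements to the Conners-3 and Vanderbilt, which Table 2 lists at baseline and 9 weeks, is not a clear gain. They too are uncontrolled, and the Conners-3 is completed by parents, while caregivers attend the intervention groups. A rule on planning the R33 phase would govern a design that these documents do not contain.

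Two side points add no weight. Section 3.4 repeats only half of the entry rule in section 3.1; this is a drafting slip to be reconciled. How the 9-week CGI-S is rated without a repeat K-SADS is not stated, which is a further reason to read the change cautiously.

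**Conclusion.** No change to the plan is called for. The CGI-S is both the qualifying score and the only pre-value of an uncontrolled exploratory outcome, so its change may include regression to the mean. The document fixes neither size nor sign. Under the assumed model the artefact is about −0.19 to +0.09 points if the 45-to-30 yield covers the CGI-S step. If it does not, the full range of −0.68 to +0.09 remains open.

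The result at risk is one clinician rating with no named analysis, in a pilot that already defers confirmation. An analyst reporting it would sensibly say that the screening score was the entry score, that there was no comparison group, and that the change is not evidence of an intervention effect. That belongs in the report and can be written without amending the protocol. Confidence is high on the structure and on the absence of any planned efficacy reading, and low on the size of the artefact.
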